COVER LETTER

Statistical Analysis Plan

ORIGINAL TITEL:

Comparison between the caudal block and other methods of postoperative pain relief in children undergoing circumcision: A prospective randomized study

This study was approved by the research ethics committee operates Institution Review Board number 70130623

The study conforms to the provisions of the Declaration of Helsinki in 1995 (as revised in Edinburgh 2000) and it was ethically approved by the Research Committee for Government Hospitals, Salmaniya Medical Complex, Kingdom of Bahrain (IRB number: 70130623).

Data management

The collected data were recorded then presented and statistically analyzed by computer using SPSS 27.0 for Windows (*SPSS Inc., Chicago, IL, USA*) and Prism Graphpad version 9.4.1 (*Graphpad, San Diego, USA*). A test of normality was done using the Kolmogorov-Smirnov test. Kruskal-Wallis test was used to compare between groups for numerical variables, while Chi-square and Fisher's Exact test were used for categorical variables. Linear regression analysis was used to detect the predictors of pain scale. All tests were two-sided. The accepted level of significance in this work was ($p \leq 0.05$). A p -value ≤ 0.01 was considered highly statistically significant and $p > 0.05$ was considered non-statistically significant.

Results

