A total of 90 patients had participated in this current study. The study subjects were classified into 3 main groups. The first group (group A) received general anesthesia with caudal block including 29 patients. The second group (Group B) represented general anesthesia with an opioid group with a total of 33 participants, while the last group (Group C) was patients with a penile block 28 patients. Group B was significantly older in comparison with the other two groups, while Group A was the youngest age group as described in Table 1. No significant difference had been observed regarding operation duration among the three groups. Sevo Mac consumption is significantly lower in group A in comparison with the other two groups. Fentanyl consumption intra and post-operative is higher in group B followed by group C, while the lowest level of consumption with among group A patients. Participants' heart rates are shown in Figure 1. Group C significantly showed a higher mean heart rate intraoperative, 5, 10, 20, 30, and 60 minutes postoperative, while group B showed the lowest mean heart rate in the three groups ($p < 0.005$). The behavioral score is represented in figure 2 which had been measured 5, 10, 20, 30, and 60 minutes postoperative. Group C significantly demonstrated a higher percentage of severe discomfort in comparison with the other two groups in 5, 10, 20, and 30 minutes post-operative (82.1, 25.0%, 21.4%, and 3.6% respectively). The percentage of severe discomfort in group B in 5, 10, 20, and 30 minutes post-operative was 18.2, 6.1%, 3.0%, and 0.0% respectively, while only one patient expressed severe discomfort in 5, 10, and 20 minutes in group A. The pain scale was much higher among group C, while group A showed the lowest mean pain scale (Figure 3).

Table 2 represents the crying scale (5, 10, 20, 30, 60 minutes postoperative) among the studied groups. Group C showed a higher percentage of crying in comparison with the other two groups, however, the relation was non-significant.

The movement scale also was significantly different between the 3 groups in 5, 20, and 30 minutes post-operative (Table 3). Similarly, a significant difference was shown between the 3 groups in the agitation scale in 5, 10, and 30 minutes postoperative (Table 4). Table 5, demonstrated a

statistically significant difference between the 3 groups on the posture scale in 5, and 30 minutes post-operative.

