Table 6 explains that the type of block, fentanyl intraoperative and postoperative was the predictor of the 5-minute pain scale, while the type of block was only the significant predictor of the 10, 20, and 30-minute pain scale. The type of block and weight of participants were the predictors of the pain scale 60 minutes postoperative

Comparison between the caudal block and other methods of postoperative pain relief in children undergoing circumcision: A prospective randomized study

This study was approved by the research ethics committee operates Institution Review Board number 70130623

Table 1. Demographic data of children who underwent circumcision

Demographic data of children who underwent circumcision Variables	Group A (n=29) Mean±SD	Group B (n=33) Mean±SD	Group C (n=28) Mean±SD	P-value*	Significant pairs**
Age (months)	16.0±7.5	41.8±43.3	16.3±19.7	0.002	Group A vs.s Group B AND Group B vs Group C
Weight (KG)	10.3±2.4	11.3±3.8	9.0±5.1		0.130
Operation duration (minutes)	14.6±3.5	15.1±4.6	16.3±6.1		0.523
Sevo mac	0.5±0.3	2.0±1.6	1.5±0.2	<0.001	Group A vs. Group B AND Group A vs. Group C
Fentanyl intraoperative	9.9±5.4	22.1±9.1	16.4±5.4	<0.001	Group A vs Group B Group A vs. Group C AND Group B vs. Group C
Fentanyl postoperative	4.8±3.1	10.5±4.6	5.2±2.5	<0.001	Group A vs. Group B AND Group B vs. Group C

Comparison between the caudal block and other methods of postoperative pain relief in children undergoing circumcision: A prospective randomized study

This study was approved by the research ethics committee operates Institution Review Board number 70130623

Table 2:

represents the crying scale (5, 10, 20, 30, 60 minutes postoperative) among the studied groups. Group C showed a higher percentage of crying in comparison with the other two groups, however, the relation was non-significant

Crying scale (5, 10, 20, 30, 60 minutes postoperative) among studied groups

Brief title: Participants' Crying Scale

[figure not shown]
Variables	Group A (n=29) N (%)	Group B (n=33) N (%)	Group C (n=28) N (%)	P -value
5 minutes postoperative				
Not crying	19 (65.5)	19 (57.6)	13 (46.4)	0.344
Crying but responds to tender Loving care	10 (34.5)	14 (42.4)	15 (53.6)	
10 minutes postoperative				
Not crying	15 (51.7)	17 (51.5)	10 (35.7)	0.375
Crying but responds to tender Loving care	14 (48.3)	16 (48.5)	18 (64.3)	
20 minutes postoperative				
Not crying	19 (65.5)	16 (48.5)	12 (42.9)	0.200
Crying but responds to tender Loving care	10 (34.5)	17 (51.5)	16 (57.1)	

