30 minutes postoperative				
Not crying	13 (44.8)	15 (45.5)	14 (50.0)	0.912
Crying but responds to tender Loving care	16 (55.2)	18 (54.5)	14 (50.0)	

60 minutes postoperative

[figure not shown]
Not crying	17 (58.6)	19 (57.6)	12 (42.9)	0.407
Crying but responds to tender Loving care	12 (41.4)	14 (42.4)	16 (57.1)	

The comparison between groups was done using Chi square test (χ^2)

[figure not shown]
5 Minutes

10 Minutes

[figure not shown]

20 Minutes

[figure not shown]

- Relaxed and comfortable
- Mild discomfort
- Moderate pain
- Severe discomfort/pain

30 Minutes

60 Minutes

Behavioral score among studied groups. *Fisher's exact test was used* FLACC scores from 0-10 , zero is analgesia, 1-3 is for mild pain, 4-6 is for moderate pain, and 7-10 is for severe pain

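### The stated between-arm pain tests use no baseline covariates, and the separate predictor regression is too loosely described to serve as a consistently adjusted comparison of the arms

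*SAP*

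**What the plan says.** The Data management section of the SAP sets a general rule for group comparisons: "Kruskal-Wallis test was used to compare between groups for numerical variables", and "Chi-square and Fisher's Exact test were used for categorical variables". The caption "Behavioral score among studied groups" adds that Fisher's exact test was used for that score. By the general rule, a numerical pain scale falls to Kruskal-Wallis.

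The same section has one sentence on modelling: "Linear regression analysis was used to detect the predictors of pain scale". It gives no covariate list. It does not say whether block and covariates are fitted together, or whether the regression or the rank test is the main comparison of the arms.

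The SAP Results report the regression by time point:

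- 5 minutes: "Table 6 explains that the type of block, fentanyl intraoperative and postoperative was the predictor of the 5-minute pain scale".
- 10, 20 and 30 minutes: "the type of block was only the significant predictor of the 10, 20, and 30-minute pain scale".
- 60 minutes: "The type of block and weight of participants were the predictors of the pain scale 60 minutes postoperative".

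Table 1 gives age and weight by arm. The Results text comments that "Group B was significantly older in comparison with the other two groups".

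**The concern.** The tests named for comparing the arms cannot take account of a baseline difference. The only analysis that could do so is presented as a hunt for predictors, not as an estimate of the block effect. A reader who wants the A-C or B-C difference in pain, allowing for the children's age and size, cannot find it as a defined quantity.

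Two things are at stake. First, part of an observed difference between arms may reflect who was in the arms, to the extent that age or weight is related to pain. Randomisation makes such differences average out over repetitions. It does not remove the one that occurred. Second, the regression's block effects may not be comparable across time. At 5 minutes the reported predictors include intraoperative and postoperative fentanyl. Both arise after allocation and differ strongly by arm (Table 1, p<0.001 for each), so a block effect adjusted for them answers a different question from one adjusted for baseline weight.

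**Working it through.** **Inputs (SAP Table 1; n = 29, 33, 28 for A, B, C)**

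| | A | B | C | Printed p |
|---|---|---|---|---|
| Age, months | 16.0±7.5 | 41.8±43.3 | 16.3±19.7 | 0.002 |
| Weight, kg | 10.3±2.4 | 11.3±3.8 | 9.0±5.1 | 0.130 |

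Not given: the pain SD, the correlation of weight or age with pain, and the Table 6 coefficients.

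**1. The plan's own figures.** A Kruskal-Wallis p-value cannot be rebuilt from means and SDs. As a plausibility check for weight, one-way ANOVA gives F = 2.63, p = 0.078, and Welch's version gives F = 1.98, p = 0.148. The printed 0.130 lies between them. For age the same two tests give p = 0.0005 and p = 0.007, consistent with the printed 0.002. An uncorrected Pearson chi-square on the Table 2 counts returns 0.344, 0.375, 0.200, 0.912 and 0.407. These match all five printed values, so the crying comparisons are unadjusted.

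**2. Size of the baseline gaps.** Pooled SD = √[Σ(n−1)s² / 87].

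- Weight: √[(28×2.4² + 32×3.8² + 27×5.1²)/87] = √(1325.63/87) = 3.90 kg. Gaps: B-C 2.3/3.90 = 0.59 SD; A-C 1.3/3.90 = 0.33 SD; B-A 1.0/3.90 = 0.26 SD.
- Age: √[(28×7.5² + 32×43.3² + 27×19.7²)/87] = √(72049.91/87) = 28.8 months. Gaps: B-A 25.8/28.8 = 0.90 SD; B-C 25.5/28.8 = 0.89 SD; A-C 0.3/28.8 = 0.01 SD in absolute size.

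**3. Effect of adjusting for weight, under an assumed within-arm correlation ρ.** Shift in a contrast = ρ × gap, in within-arm pain SDs. Residual variance is multiplied by 1 − ρ².

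| ρ (assumed) | Residual variance | Shift B-C | Shift A-C | Shift A-B |
|---|---|---|---|---|
| 0.2 | 0.96 | 0.12 | 0.07 | 0.05 |
| 0.3 | 0.91 | 0.18 | 0.10 | 0.08 |
| 0.4 | 0.84 | 0.24 | 0.13 | 0.10 |

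The sign of ρ is not given, so the direction of the shift is unknown. For orientation, p ≤ 0.05 for a covariate with about 85 degrees of freedom needs a partial correlation of t/√(df+t²) = 1.988/√(85+3.95) = 0.21. That is a threshold for the observed value, not a lower bound for the true one.

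**4. What this is worth in precision.** For an assumed A-C difference of 0.75 SD (29 v 28), power rises from 0.808 to 0.824 at ρ = 0.2 and 0.843 at ρ = 0.3. This leaves out a small penalty: when arms are imbalanced, the variance of an adjusted contrast is multiplied by 1 + gap²/[S(1/n₁+1/n₂)], where S is the pooled sum of squares.

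- Weight, A-C: 1 + 1.3²/(1325.63×0.0702) = 1.02.
- Weight, B-C: 1 + 2.3²/(1325.63×0.0660) = 1.06.
- Age alone, B-A: 1 + 25.8²/(72049.91×0.0648) = 1.14.

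For B-C at ρ = 0.2 the net weight factor is 0.96×1.06 = 1.02, which is no gain. At ρ = 0.4 it is 0.84×1.06 = 0.89.

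**5. A reason to check Table 1 first.** The protocol abstract limits age to 3 months to 3 years, that is, 36 months at most, yet Group B's mean age is 41.8 months. Group B is also 25.8 months older than Group A on average but only 1.0 kg heavier. Either row could contain an error.

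**The case against.** The strongest reply is that weight was not ignored. A reader might infer from the named tests that the pain analysis disregards weight at every time, or that weight adjustment was switched on and off by its p-value. The documents support neither. A pain regression exists, and at 60 minutes it names block and weight together. Its summary lists the significant terms, not the terms fitted. It is compatible with one multivariable model at all five times, in which case every block effect in it is already weight-adjusted. It is equally compatible with univariable or stepwise fits. Table 6 itself is not in the text, so this cannot be settled.

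Other parts of the reply also stand. If randomisation was valid, the unadjusted tests are valid, and leaving out a covariate mainly costs efficiency. The weight imbalance is compatible with chance (p = 0.130), although that does not show balance. Weight is reported as a predictor only at 60 minutes, and block is still reported as a predictor beside it. Age is the more imbalanced variable. Results at all five times are already known, so choosing covariates now is post hoc. No outcome, time or test is named as primary, so the documents do not say which pain comparison is the main one.

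What the reply does not meet is the missing definition. Nothing in the SAP says which covariates enter, whether they are fitted with block, or which result is to be read as the arm comparison.

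**Conclusion.** The point holds as a worthwhile improvement of modest size. The named between-arm tests are unadjusted, and the regression as described cannot stand in for a consistently adjusted comparison.

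The size rests on an assumed weight-pain correlation of 0.2 to 0.4. That gives 4% to 16% less residual variance, with shifts of 0.12 to 0.24 SD in B-C and 0.07 to 0.13 SD in A-C, direction unknown. The net gain in precision is smaller for contrasts involving Group B because of the imbalance penalty. There the case for adjustment is mainly that it accounts for the difference that occurred. No figure can be put on the effect of age, since no age-pain relation is reported.

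Nothing here shows that the large early differences between arms would disappear after adjustment, or that the unadjusted tests are invalid.

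**What to change.** 1. Verify the ages and weights in Table 1 against source data.
2. Estimate the arm effect on the pain scale at 5, 10, 20, 30 and 60 minutes from one model form containing arm, baseline age and baseline weight. Keep the same covariates at every time, whatever their p-values. Use a proportional-odds model if the score is skewed.
3. Leave intraoperative and postoperative fentanyl out of that model, since both follow allocation.
4. Report each pairwise arm effect with its confidence interval, with Kruskal-Wallis alongside as the unadjusted result.
5. Label the adjusted analysis post hoc, because the results are already known.
6. State the covariate list and form of fitting for Table 6, and do not present weight as a finding in its own right.

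The cost is a paragraph of SAP wording, one re-run on data already collected, and two degrees of freedom out of 90 children.

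### The behavioural score has four ordered levels but is compared with Fisher's exact test, which ignores the order and, under an assumed moderate ordered shift, costs roughly 13 to 21 points of power

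*SAP*

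**What the plan says.** The SAP's Data management section sorts variables into two kinds. Kruskal-Wallis "test was used to compare between groups for numerical variables"; Chi-square and Fisher's "Exact test were used for categorical variables". No rank, trend or proportional-odds method is named for categories that have an order. Also: "All tests were two-sided", with significance at p of 0.05 or below.

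The SAP Results text introduces the score: "The behavioral score is represented in figure 2 which had been measured 5, 10, 20, 30, and 60 minutes postoperative". The legend of that figure lists four levels, from relaxed to severe, ties them to FLACC ("zero is analgesia, 1-3 is for mild pain, 4-6 is for moderate pain, and 7-10 is for severe pain"), and states that Fisher's "exact test was used".

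The Results text then makes a directional claim: group C (penile block) had significantly more severe discomfort than the other two groups at 5, 10, 20 and 30 minutes. It gives no behavioural result for 60 minutes. Neither document states a target effect or a sample-size calculation, and the full four-level distribution is only in the figure, which is not available here.

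**The concern.** The trial asks which method leaves children in less pain. That is a question about a shift along an ordered scale. Fisher's exact test on a groups-by-levels table responds to any departure from equal distributions and gives no extra weight to a consistent move towards worse pain. If the true difference is such a move, some of the information in 90 children goes unused.

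Two things are at stake: the chance of detecting a difference where effects are smaller, and the support for pairwise, directional statements about group C. An omnibus nominal p-value does not supply that support.

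**Working it through.** **1. Inputs from the SAP.** Group sizes 29 (A, caudal), 33 (B, opioid), 28 (C, penile block), N = 90; two-sided alpha 0.05; four ordered levels. The reported severe percentages match whole counts:

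| Minutes | A | B | C |
|---|---|---|---|
| 5 | 1/29 (3.4%) | 6/33 (18.2%) | 23/28 (82.1%) |
| 10 | 1/29 (3.4%) | 2/33 (6.1%) | 7/28 (25.0%) |
| 20 | 1/29 (3.4%) | 1/33 (3.0%) | 6/28 (21.4%) |
| 30 | not stated | 0/33 (0.0%) | 1/28 (3.6%) |

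There is no design power figure to reproduce.

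**2. Why order is lost.** With margins fixed, the exact probability of a table is (product of row totals! x product of column totals!) / (N! x product of cell counts!). Swapping two columns changes nothing, so the p-value is the same if severe and relaxed trade places. Kruskal-Wallis uses mid-ranks of the levels: H = [12/(N(N+1))] x sum(R_g^2/n_g) - 3(N+1), divided by the tie correction 1 - sum(t_j^3 - t_j)/(N^3 - N), referred to chi-square on 2 df.

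**3. Power under an assumed ordered shift.** Model: logit P(level at or below j) = a_j - b_g. Assumed baselines for A: 25/25/25/25, 40/30/20/10, 60/25/10/5 and 70/20/7/3 percent. Assumed patterns: B equal to A, or B halfway to C on the log-odds scale. Fisher p-values came from 999 random tables with fixed margins per simulated trial, with 2,000 trials per scenario (standard error at most sqrt(0.25/2000) = 1.1 points). Ranges are over the eight baseline-by-pattern scenarios.

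| Odds ratio, C vs A | Fisher | Kruskal-Wallis | Loss (points) |
|---|---|---|---|
| 1 (type I error) | 4-6% | 4-6% | about 0 |
| 2 | 13-20% | 20-30% | 6-11 |
| 3 | 30-45% | 45-66% | 13-21 |
| 4 | 47-69% | 65-85% | 16-20 |
| 6 | 74-92% | 89-97% | 6-15 |
| 10 | 93-99% | 98-100% | 1-6 |

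At odds ratio 4 with B equal to A, Kruskal-Wallis has 81-85% power and Fisher 64-69%, a loss of 16 to 19 points.

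**4. Scenarios set close to the reported severe percentages** (other three levels, and A at 30 minutes, assumed; 3,000 trials each):

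| Minutes | Fisher | Kruskal-Wallis | Loss (points) |
|---|---|---|---|
| 5 | 100% | 100% | 0 |
| 10 | 74% | 87% | 13 |
| 20 | 79% | 88% | 9 |
| 30 | 38% | 52% | 15 |

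**5. Non-ordered alternatives.** With A and B at 40/30/20/10 and C at 30/20/15/35, where the middle levels thin out and severe rises, Fisher has 49% and Kruskal-Wallis 39%. With A and B at 25/25/25/25 and C at 45/5/5/45, a pure difference in spread, it is 86% against 6%. The advantage reverses by 10 and 80 points.

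**6. What the severe category alone supports.** Exact tests of severe versus not severe across the three groups give p < 0.001, p = 0.03 and p = 0.02 at 5, 10 and 20 minutes. At 30 minutes, with A at 0, the single event falls in C with probability 28/90 = 0.31, in A with 29/90 and in B with 33/90. C is the least likely, so p = 0.31. With A at 1, p = 0.53. Two or more in A (2/29 = 6.9%) would contradict C being highest. So significance at 30 minutes cannot come from the severe level alone; it must draw on the other levels.

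Pairwise and unadjusted, severe versus not: at 10 minutes C vs A p = 0.025 and C vs B p = 0.067; at 20 minutes C vs A p = 0.052 and C vs B p = 0.041.

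**The case against.** **No reported conclusion is shown to change.** Lost power matters when a real difference is missed, and the Results text already claims significance at 5, 10, 20 and 30 minutes. This stands. It confines the gain mainly to 60 minutes and to pairwise contrasts, and a missed difference at 60 minutes cannot be demonstrated.

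**The size is assumed.** A reader might infer that the test gives up a fixed 15 to 20 points. The documents do not support that: there is no target effect and no visible distribution. The reported severe counts also imply effects outside the moderate range. The C versus A odds ratios for severe are (23/5)/(1/28) = 129, (7/21)/(1/28) = 9.3 and (6/22)/(1/28) = 7.6 at 5, 10 and 20 minutes, imprecise as they are. The size therefore has to be stated with its conditions.

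**Kruskal-Wallis is an omnibus test too.** Correct. It does not say which group is worse, so changing the overall test is not enough without pairwise comparisons.

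**Pain is analysed in ordered form elsewhere.** The Results text describes a pain scale by group means and regressions in which type of block predicts the pain scale at every time point, including 60 minutes. This lowers the stakes, but the behavioural score is presented as its own result, with its own test and directional claim.

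**Sparse cells favour an exact test.** Counts of 0 and 1 are a good reason for exactness, and they could make a proportional-odds model unstable. They are not a reason to discard order.

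**Conclusion.** The point holds in a conditional form. The levels are ordered by the SAP's own FLACC bands, and the named test ignores that order. This takes the test to have been run on the full three-by-four table, which the legend does not spell out but which fits the 30-minute result. Under an assumed proportional-odds shift with odds ratio about 3 to 4, the loss against Kruskal-Wallis is roughly 13 to 21 points. It is smaller for small or very large effects, nil at the 5-minute effect, and can reverse if the difference is not a shift.

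A reader might also infer that Fisher's test is invalid here, or that the reported findings are wrong. Neither follows: type I error is near 5% for both tests, and the significance reported at 5 to 30 minutes is not overturned. The change is worth making because it is nearly free and fits the question, chiefly for 60 minutes and for the pairwise claims about group C.

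**What to change.** In Data management, state that ordered categories, including the behavioural score, are compared between groups with Kruskal-Wallis on the ordered levels, followed by multiplicity-adjusted pairwise rank comparisons (A vs B, A vs C, B vs C), so that statements about group C rest on a test of them. Where cells are not too sparse, add a proportional-odds model with group as a three-level factor and report pairwise odds ratios with 95% confidence intervals. Keep Fisher's exact test for binary or truly nominal tables. Report the behavioural result at 60 minutes in the text. Because the SAP already contains results, show the ordinal analysis beside the Fisher result and say that it was added afterwards.

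Cost: a few sentences and a re-run on existing data, with the overall test already in the plan. The downsides are less power against non-monotone differences and possible instability of the proportional-odds model where cells are 0 or 1.
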